## **1.0 BACKGROUND AND SIGNIFICANCE**

The principal goals for the study are to examine 1) how long after ingestion of a single sweetened beverage are levels of that sweetener still elevated, and 2) whether ingestion of a beverage containing either an artificial sweetener or glucose alters *in vitro* platelet aggregation.

Due to the growing number of cardiometabolic diseases like diabetes mellitus, the use of polyols (a.k.a. sugar alcohols) and other artificial sweeteners to replace free sugars has recently gained increasing appreciation. Two popular artificial sweeteners are erythritol and xylitol.

Erythritol and xylitol are both naturally occurring polyols found in fruits and vegetables. They are potent artificial sweeteners with a higher sweetening intensity and lower calorie content than table sugar. This makes them attractive for the use as sugar substitutes or alternatives, particularly for patients with type 2 diabetes.

All three mentioned sweeteners are generally considered safe and approved by the Food and Drug Administration (FDA) as food additives. Major side effects of excessive consumption comprise flatulence, laxation, and headache. Erythritol and xylitol are well tolerated up to an intake of 60g and 50g daily, respectively (1, 2). Major side effects of glucose are insulin resistance and type 2 diabetes following excessive chronic consumption.

Up to now, there is no prospective data available about polyols with respect to their impact on event outcomes in cardiovascular patients, despite the extensive use in the food industry. Moreover, little is known about plasma levels and metabolic changes following food intake of artificial sweeteners, in particular polyols.

We have measured fasting levels of various polyols in a large clinical cohort of cardiovascular patients and found that some candidate polyols are related to a higher risk of cardiovascular complications and death. *In vitro* data using human platelets revealed that the polyols xylitol and erythritol at the levels observed in fasting patients

induce platelet aggregation potential. Our data shows that erythritol and xylitol, impact platelet function and thereby may contribute to cardiovascular mortality.

In preliminary studies we found that upon ingestion erythritol and xylitol levels in the plasma rise within the first hour. With this study we wish to examine whether the postprandial levels are capable of altering platelet function *in vitro*. We hypothesize that post prandial polyol concentrations following ingestion increase platelet aggregation in the blood.

Glucose, as a naturally occurring sweetener, will serve as a control for this study. There is also evidence that glucose may increase platelet aggregation, allowing us to compare the degree of increased aggregation between the polyol sweeteners and glucose. (3)

## 2.0 STUDY OBJECTIVES

To assess platelet function before and after polyol exposure.

## 3.0 STUDY DESIGN

We will perform a prospective, non-blinded, 4-arm study. There will be up to 8 study visits depending on which arm the subject is assigned to. There will be three interventions: erythritol, xylitol, and glucose. Erythritol and glucose will each be used in one arm, xylitol will be used in two arms.

At baseline, subjects will have fasting blood and urine samples collected. Subjects will then receive a drink (300mL of water containing either 30g of erythritol, 30g of xylitol, 5g of xylitol, or 30g of glucose) as a single oral dose. Blood and urine samples will be collected again on the same day at pre-determined intervals after ingestion of the sweetened water drink. Additional fasting blood and urine samples may be collected on subsequent days after drinking the artificially sweetened water as shown in the tables below. Subjects drinking xylitol (5g or 30g) may have 1 subsequent visit. Subjects consuming erythritol may have up to 7 subsequent visits. Subjects consuming glucose will have 1 study visit with blood and urine being collected about 30 minutes apart. All fasting collections will occur after an 8+ hour fast.

Xylitol schedule (5g and 30g):

	Visit 1 Day 1	Visit 2 Day 2
Informed Consent	X	
Brief Medical History Questionnaire	X	
Vital Signs	X	

Baseline Fasting Blood Collection	X	X
Baseline Fasting Urine Sample	X	X
Drink Sweetened Water	X	
30 minutes Post-drink Blood & Urine Collection*	X	
1 hour Post-drink Blood & Urine Collection*	X	
4 hours Post-drink Blood & Urine Collection*	X	
6 hours Post-drink Blood & Urine Collection*	X	

Erythritol schedule:

	Vital Signs	Medical History	Blood Draw	Spot Urine Sample
Baseline	X	X	X	X
+ 30 minutes			X	X
+ 2 hours*			X	X
+ 6 hours*			X	X
+ 24 hours (Day 2)*			X	X
+ 48 hours (Day 3)*			X	X
+ 72 hours (Day 4)*			X	X
+ 96 hours (Day 5)*			X	X
+ 168 hours (Day 8)*			X	X
+ 216 hours (Day 10)*			X	X
+ 264 hours (Day 12)*			X	X

Glucose schedule:

	Vital Signs	Medical History	Blood Draw	Spot Urine Sample
Baseline	X	X	X	X
+ 30 minutes			X	X

\* Laboratory schedules are subject to change as data is gathered. Subjects will be informed of lab schedule at time of consent.

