## 8.2 Serious/Unexpected Adverse Events

Serious and unexpected adverse events will be reported to the Ethical Committee in accordance with institutional guidelines. In the case there would be any adverse events or unanticipated problems, an appropriate adverse event or unanticipated report form will be made and the Ethical Committee notified immediately. The study will also be stopped immediately if a subject would experience any unanticipated discomfort or adverse cardiac events (e.g. hospitalization). There will be no DMC and no interim analyses.

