### **Outcomes**

### **Primary Outcomes**

- Polyol levels (erythritol and xylitol) in the blood quantified using established techniques by mass spectrometry.
- Polyol levels (erythritol and xylitol) in the urine quantified using established techniques by mass spectrometry.
- · changes in platelet function throughout the study using well established in vitro platelet assays

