## Statistical analysis Plan for Primary outcomes

- Erythritol concentration in the blood at various time points will be analyzed by ANOVA analysis or Student t-test/Wilcoxon test as
  appropriate. Type I error will be controlled for though adjustment for multiple testing as appropriate. A P value <0.05 will be considered
  significant.

- 2. Erythritol concentration in the urine at various time points will be normalized to urine creatinine levels: erythritol urine/ creatinine urine. Levels will be analyzed by ANOVA analysis or Student t-test/Wilcoxon test as appropriate. Type I error will be controlled for though adjustment for multiple testing as appropriate. A P value <0.05 will be considered significant.
- 3. Platelet functional changes before and after xylitol/erythritol drink will be analyzed by ANOVA analysis or Student t-test/Wilcoxon test as appropriate. Type I error will be controlled for though adjustment for multiple testing as appropriate. A P value <0.05 will be considered significant.

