# **Hypothesis testing**

For aim 1, we will test the hypothesis that post prandial levels of erythritol or xylitol (after 30g ingestion) exceed fasting levels. Testing will be performed by comparing post prandial erythritol levels with fasting levels in each individual.

For aim 2, we will test the hypothesis that post prandial levels of erythritol and xylitol alter platelet function. Testing will be performed by comparing markers for platelet function before and after exposure to xylitol or erythritol.

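### Does the primary platelet outcome need one fixed assay, time and adjustment family, given that the draw schedule may change?

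*Protocol*

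**What the plan says.** The SAP (Primary Outcomes) lists three primary outcomes: polyol levels in blood, polyol levels in urine, and "changes in platelet function throughout the study using well established in vitro platelet assays". For the third, Statistical analysis Plan for Primary outcomes states: "Platelet functional changes before and after xylitol/erythritol drink will be analyzed by ANOVA analysis or Student t-test/Wilcoxon test as appropriate". It adds: "Type I error will be controlled for though adjustment for multiple testing as appropriate". Under Hypothesis testing, aim 2 reads: "Testing will be performed by comparing markers for platelet function before and after exposure to xylitol or erythritol". None of these sections names an assay, a post-dose time, an adjustment method or a family of tests.

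Protocol 3.0 gives the draw schedules. Post-dose draws number 10 for erythritol (30 minutes, 2 and 6 hours, then seven later days), 5 for xylitol (30 minutes, 1, 4 and 6 hours, then Day 2) and 1 for glucose (30 minutes). The xylitol row "30 minutes Post-drink Blood & Urine Collection" is starred; the 30-minute rows for erythritol and glucose are not. The star leads to the footnote "Laboratory schedules are subject to change as data is gathered", and the next sentence says that subjects learn their schedule when they consent. On the later days, "Additional fasting blood and urine samples may be collected on subsequent days".

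The SAP's Study Design text sets a repeat collection 30 minutes after the drink for both polyols and leaves other times to the tables. Protocol 8.2 and the matching SAP section state: "There will be no DMC and no interim analyses".

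**The concern.** A primary outcome with several unnamed assays, up to ten post-dose times, three permitted kinds of test and an unspecified adjustment can be analysed in many ways. A reader cannot check that error is controlled, and a cautious analyst who adjusts over every draw gives up power.

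The footnote adds to the worry. The study is not blinded, and the text does not say which accumulating data may change the schedule. If platelet results did so, the analysis times would be chosen partly on the outcome. The statement on interim analyses sits in the safety section and is not linked to the footnote.

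The xylitol star matters because 30 minutes is the only post-dose time shared with glucose. Protocol 1.0 intends to compare aggregation between the polyols and glucose. If the xylitol draw moved, that comparison would have no matched time.

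**Working it through.** **The plan's own figure.** Protocol 7.1 and the SAP give n = 10, power 0.9 and significance level 0.05. They give no endpoint, effect, SD or test, so n cannot be derived forward. Solving backwards with a two-sided noncentral t:

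- paired, n = 10: standardised change d = 1.155;
- two groups of 10: d = 1.534.

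The wording refers to a difference between groups, so applying it to a paired platelet change is an assumption. So is the assumption that platelets are assayed at every draw.

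**Power for a change at 30 minutes.** Power = P(|T| > t(1 − 0.05/(2k), n − 1)), where T is noncentral t with n − 1 degrees of freedom and noncentrality d√n, and k is the number of draws in a Bonferroni family. Protocol 6.0 aims for at least 12 completers per polyol cohort. Protocol 7.1 plans at least 15 enrolled. The noncentrality is 1.155 × √12 = 4.00 and 1.155 × √15 = 4.47.

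| Family | k | n = 12 | n = 15 |
|---|---|---|---|
| one fixed test | 1 | 95.3% | 98.6% |
| same-day erythritol | 3 | 85.7% | 94.5% |
| same-day xylitol | 4 | 82.1% | 92.8% |
| all xylitol | 5 | 79.1% | 91.1% |
| all erythritol | 10 | 68.2% | 84.7% |

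On the two-group reading, 12 per group gives 94.8%, 86.7%, 83.9%, 81.4% and 72.9%.

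**Other analyses the SAP allows.** The table assumes an effect at 30 minutes only and the bluntest correction. Two alternatives:

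- *Omnibus repeated-measures ANOVA* (one test, Greenhouse-Geisser corrected, simulated, same 30-minute effect, n = 12). With equally correlated draws, power is 97%, 96% and 91% for 3, 5 and 10 draws. If correlation decays by a factor of 0.7 per draw, it is 89%, 67% and 30%.
- *Holm*, n = 12, correlation 0.5, same effect at every draw (the favourable end). Power at 30 minutes is 93%, 92%, 90% and 84% for 3, 4, 5 and 10 draws.

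**Type I error.**

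- Unadjusted and independent, 5 draws give 1 − 0.95^5 = 22.6% and 10 give 1 − 0.95^10 = 40.1%. The SAP promises adjustment, so these are not its error rates. Bonferroni over all listed draws gives 2.9% to 5.0% in simulation at n = 12.
- Suppose platelet results of the first 4 to 6 of 12 subjects drove the schedule, and adjustment covered only two kept draws (the unstarred one and the best starred one). At correlation 0.5 the error would be 6.0% to 6.5% (3 draws), 7.1% to 8.3% (5) or 8.4% to 11.0% (10). The highest value, with 10 independent draws, is 13.7%. This requires an interim look that the plan excludes, and an adjustment that ignores the discarded draws.

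**The passages side by side.** Protocol 1.0 gives as its first goal how long sweetener levels stay raised. Refining draw times on concentration data serves that goal and involves no look at platelet results, so the footnote and the exclusion of interim analyses are compatible. Because each subject is told the schedule at consent, changes most naturally apply to later enrollees. The xylitol star is at odds with the SAP's Study Design text, which already specifies the 30-minute sample.

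**The case for a change.** The strongest case for a change is that the plan uses confirmatory terms (90% power and P < 0.05 on primary outcomes) for an outcome whose test is not defined. At the 12-completer goal, the choice of family alone moves power between 95% and 68%. An omnibus test does not rescue every case: with fading correlation and ten draws its power falls to 30%, and it does not say when the change occurs. Naming one assay, the 30-minute time and one paired test would cost only text.

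Much of this stands as description. The assay, time and family are indeed not stated, and the xylitol star is inconsistent. But the proposed narrowing has costs of its own.

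- It would discard, as primary evidence, any effect that appears later or in another assay. Protocol 1.0 supports an early time only in reporting that plasma levels rise within the first hour.
- Testing at 0.05 in each of the six polyol cells (three arms by two cohorts) leaves 1 − 0.95^6 = 26.5% for a claim resting on any one of them, if they are independent. It also leaves open the three primary outcomes: 1 − 0.95^3 = 14.3% if independent and unadjusted.
- The glucose comparison is not tested in the SAP, which covers the two polyols only.

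The decay factor of 0.7 per draw is also arbitrary for erythritol gaps that run from 30 minutes to 72 hours.

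**Conclusion.** The gap is real but does not call for a change. The study is described as a pilot, Protocol 1.0 points to aggregation as the measure of interest, and the SAP commits to adjustment and to a 30-minute sample. An analyst can choose the assay, the paired comparison and the family within those limits. A sentence barring platelet results from driving the schedule would restate what the exclusion of interim analyses already implies. Removing the xylitol star would tidy a slip, but would change no result unless the sponsor moved a draw that the SAP text already specifies. Narrowing to one time and one assay is a debatable trade-off, not a correction.

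On size: with 15 per cell, Bonferroni over 3 to 5 draws keeps 91% to 95% power, above the stated 90%. With 12, it gives 86% to 79%, and 68% over ten draws. The equal-correlation ANOVA stays at 91% or more. The shortfalls come from the cautious Bonferroni choice at 12 completers (or over ten draws) and from the fading-correlation ANOVA. The inflated error rates come only from dropping the promised adjustment or looking at platelet data early.

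All power figures are illustrative. They rest on reading n = 10 as a paired platelet change and on assays at every draw, neither of which the documents state.

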### 3.1 Study endpoints

- Baseline plasma and urine fasting polyol or glucose

- Baseline and subsequent (after sweetener intake) changes in levels of polyol or glucose in plasma and urine as measured by established techniques by mass spectrometry.
  - Baseline and subsequent (after sweetener intake) changes in platelet function throughout the study using well established in vitro platelet assays.
- Changes in markers of metabolism (e.g. lipid profile).

#### **4.0 SUBJECT SELECTION AND WITHDRAWAL**

There will be two study cohorts for the polyol arms. We will enroll healthy control subjects in the glucose arm. Subjects must meet the following inclusion/exclusion criteria to be eligible for the study.

##### 4.1 Cohort 1 Inclusion Criteria

- Men and women age 18 years or above.
- Able to provide informed consent and comply with study protocol.

##### 4.2 Cohort 1 Exclusion Criteria

- Use of anti-platelet medications within 14 days of study enrollment.
- Active infection or received antibiotics within 1 month of study enrollment.
- Use of OTC probiotic within 1 month of study enrollment.
- Diabetes Mellitus
- Ulcerative colitis, Crohn's disease, or other chronic gastrointestinal disorder.
- Past history of bariatric procedures or surgeries (e.g. gastric banding or bypass).
- Pregnancy.
- Significant chronic illness.
- Any condition that, in the judgment of the Investigator, would place a subject at undue risk by being enrolled in the trial or cause inability to comply with the trial.

##### 4.3 Cohort 2 Inclusion Criteria

- Men and women age 18 years or above.
- Able to provide informed consent and comply with study protocol.
- Diabetes Mellitus Type II

#### 4.4 Cohort 2 Exclusion Criteria

- Use of anti-platelet medications within 14 days of study enrollment.
- Active infection or received antibiotics within 1 month of study enrollment.
- Use of OTC probiotic within 1 month of study enrollment.
- Ulcerative colitis, Crohn's disease, or other chronic gastrointestinal disorder.
- Past history of bariatric procedures or surgeries (e.g. gastric banding or bypass).
- Pregnancy.
- Any condition that, in the judgment of the Investigator, would place a subject at undue risk by being enrolled in the trial or cause inability to comply with the trial.

#### 4.5 Subject Recruitment and Screening

Subjects will be recruited from the Cleveland, OH area. Subjects will be recruited by several methods, including (but not limited to) posted advertisements, chart review, and personal interactions with patients in the cardiology outpatient departments at the Cleveland Clinic Foundation. All advertising materials used for this study will be approved by the Cleveland Clinic IRB prior to dissemination.

#### 4.6 Subject Consent

Written consent will be obtained from all subjects prior to any study procedure being performed. Participants will be provided with a copy of the signed consent form. Consent will also be documented in the subject's medical record in EPIC.

#### 4.7 Early Withdrawal of Subjects

Subjects may withdraw from the trial at any time and for any reason. Some possible reasons for early withdrawal include the following:

- Development of a medical condition or need for concomitant treatment that precludes further participation in the trial
- Removal from the trial by the investigator in the best interests of the subject
- Development of an active infection or starting an antibiotic treatment regimen
- Study completion or discontinuation prior to participant completion
- Subject withdraws consent to continued participation in the trial

## **5.0 STUDY DRUG/FOOD ADDITIVE**

### **5.1 Description**

Erythritol and xylitol supplements: The brand of supplements to be used is NOW Foods. These will be obtained from a commercial source, either Amazon.com or a pharmacy/store carrying this brand and stored as below.

Glucose: The brand of glucose is NOW Foods. We will obtain from Amazon.com or a pharmacy/store carrying this brand. It will be stored at room temperature in a sealed bag.

### **5.2 Treatment Regimen**

The study additive – erythritol, xylitol, or glucose – will be dissolved in 300mL of water and given to the subjects as a water solution to be taken all at once by mouth. The 300mL of water will contain either 30g of erythritol, 30g of xylitol, 5g of xylitol, or 30g of glucose depending on the intervention the subject is assigned to.

### **5.3 Subject Compliance Monitoring**

Subjects will be observed taking their assigned intervention, either erythritol, xylitol, or glucose solution, by a study coordinator or other study personnel during their visit to ensure the subjects consume the entire beverage and are able to comply with the study procedures.

### **5.4 Storage**

Erythritol, xylitol and glucose supplements will be stored at room temperature in a dry location. They will be kept locked in a secure location. Temperature will be monitored and recorded weekly to make sure that the temperature remains between 15° and 30° Celsius.

## **6.0 STUDY PROCEDURES**

This is a prospective pilot study. Up to 105 subjects will be enrolled in this pilot study, with a goal of having at least 12 subjects in each cohort of the polyol sweetener arms & 12 subjects in the glucose arm complete the study.

## 6.1 Study Visit Procedures

- Blood Draws
- Spot Urine collections
- Medical History
- Medication Review
- Physical Exam including blood pressure, height, weight, and waist circumference

## 7.0 STATISTICAL PLAN

### 7.1 Sample Size Determination

Based on previous research, we calculate that a sample size of 10 will provide us with a power of 0.9 to detect a significant difference between groups at a significance level of 0.05. However, we plan to enroll at least 15 subjects in each cohort in each arm in order to compensate for any unexpected occurrences or subject dropouts.

### 7.2 Statistical Methods

We plan to use standard descriptive statistics to characterize the overall study population of interest both at baseline and during follow-up. Summary statistics such as means, medians, standard deviations, and ranges will be produced for measured variables, and compared within and between groups with chi-square, Student t-test/Wilcoxon test, or ANOVA analysis as appropriate. Graphical methods will be used extensively to examine distributions, identify potential influential points, and guide in data transformations if warranted.

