### Addendum

### History of additional changes of the study protocol or related documents

Protocol changes to version date 06/07/2021

- Removal of stool sample collection.
- Sample collection schedule has been modified to add more time points for blood collection.
- Subjects will no longer be randomized to their study treatment (polyol). Separate consents will be used for each polyol.
  - We no longer wish to randomize subjects in a 1:1 fashion because equal numbers of subjects in each arm may not be
     necessary to complete the planned studies. Additionally, subjects consuming xylitol will have a larger amount of blood drawn.
- We are adding a second cohort of subjects with diabetes mellitus to compare the effects of polyols in diabetics versus non-diabetics.

Consent form for Erythritol arm changes to version date 03/25/2022:

Increase in the maximum blood draw volume for Day 1.

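### Between-group platelet comparisons do not say whether post-drink values or changes are compared, and do not use the fasting value as a covariate

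*Protocol*

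**What the plan says.** **Methods named.** Protocol 7.2 says summaries will be "compared within and between groups with chi-square, Student t-test/Wilcoxon test, or ANOVA analysis as appropriate". The SAP repeats this family of tests for demographics, primary outcomes and secondary outcomes. For platelets it says: "Platelet functional changes before and after xylitol/erythritol drink will be analyzed by ANOVA analysis or Student t-test/Wilcoxon test as appropriate". Neither document names a covariate, an analysis of covariance (ANCOVA), a regression or a mixed model.

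**Use of the fasting value.** Protocol 3.1 lists the endpoint as "Baseline and subsequent (after sweetener intake) changes in platelet function throughout the study using well established in vitro platelet assays". The SAP (Hypothesis testing) tests aim 2 by "comparing markers for platelet function before and after exposure to xylitol or erythritol". These tests are within-subject and use the fasting reading.

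**Between-group aims.** Protocol 1.0 adds glucose, "allowing us to compare the degree of increased aggregation between the polyol sweeteners and glucose". The SAP Addendum says the second cohort was added "to compare the effects of polyols in diabetics versus non-diabetics". Protocol 7.1 also frames the sample size as a difference between groups. No section says which quantity is compared across groups.

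**Design.** Protocol 3.0 has fasting blood drawn from every subject at baseline. The glucose arm has only that draw and one at 30 minutes. For the polyol arms, "Additional fasting blood and urine samples may be collected on subsequent days". Protocol 6.0 aims for at least 12 completers in each polyol cohort and in the glucose arm. The SAP Addendum records that randomisation between polyols was dropped, and the SAP Study Overview has enrolment one polyol at a time. The SAP Study Design covers only erythritol and xylitol at up to 30 g, so for glucose and 5 g xylitol Protocol 7.2 is the only analysis text.

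**The concern.** With about 12 subjects per group, between-group contrasts will be the least precise results in the study. Three ways of handling the fasting value fit the present wording or are close to it: compare post-drink values, compare changes, or adjust for the fasting value. They differ in precision, and which of the two simple options is better depends on a correlation that the documents do not give. If the choice stays open, the analyst may take the weaker option or choose after seeing the data.

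The arms are also not randomised and are filled at different times, so fasting platelet values may differ between them. The handling of the fasting value can then move the estimate as well as its interval.

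**Working it through.** **The plan's own figure.** Protocol 7.1 and the SAP state that a sample size of 10 gives power 0.9 at level 0.05. No effect size, SD, test or sidedness is given, so the figure cannot be reproduced, only inverted. With 10 per group, a two-sided two-sample t-test has 90% power at a difference of about 1.53 SD (1.45 by the normal formula). If 10 is the number of pairs, the standardised mean change is about 1.155. Neither tells us the correlation needed below.

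**Inputs.**
- n = 12 per group (Protocol 6.0).
- Two-sided alpha 0.05 (level from Protocol 7.1; sidedness assumed).
- r = correlation of fasting with post-drink value: not in the documents, assumed 0.3 to 0.8.
- Equal SD before and after the drink, set to 1, and equal expected baselines in the two groups (both assumed).

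**Residual variances.**
- Post-drink value only: 1.
- Change score: 2(1 − r).
- Baseline-adjusted: (1 − r²) × [1 + 1/(2n − 4)]. The bracket is the small-sample cost of estimating the slope: 1 + 1/20 = 1.05. Error degrees of freedom fall from 22 to 21.

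Adjusted relative to change is therefore 1.05 × (1 + r)/2. Without the factor 1.05 the ratios at r = 0.5, 0.7 and 0.8 would read 0.75, 0.85 and 0.90, which overstates the gain at this sample size.

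| r | Change | Adjusted | Adjusted/change | Adjusted/post | 12 perform like (vs change) |
|---|---|---|---|---|---|
| 0.3 | 1.40 | 0.956 | 0.68 | 0.96 | 17.6 |
| 0.5 | 1.00 | 0.788 | 0.79 | 0.79 | 15.2 |
| 0.7 | 0.60 | 0.536 | 0.89 | 0.54 | 13.4 |
| 0.8 | 0.40 | 0.378 | 0.945 | 0.38 | 12.7 |

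The last column is 12 divided by the adjusted/change ratio, for example 12/0.7875 = 15.2.

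**Power for a true difference of 1.0 SD, and difference detectable with 90% power (SD), each as post / change / adjusted.**

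| r | Power | Detectable difference |
|---|---|---|
| 0.3 | 0.65 / 0.51 / 0.67 | 1.39 / 1.64 / 1.36 |
| 0.5 | 0.65 / 0.65 / 0.75 | 1.39 / 1.39 / 1.23 |
| 0.7 | 0.65 / 0.86 / 0.89 | 1.39 / 1.07 / 1.02 |
| 0.8 | 0.65 / 0.96 / 0.97 | 1.39 / 0.88 / 0.85 |

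Simulation with 4,000 trials agreed: 0.65 / 0.65 / 0.75 at r = 0.5 and 0.65 / 0.86 / 0.90 at r = 0.7.

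Change scores beat post-drink values only when 2(1 − r) < 1, that is r > 0.5. The adjusted model is at least as precise as either across 0.3 to 0.8. It loses to post-drink values only when 1.05(1 − r²) > 1, that is r below about 0.22, and then by at most 5%.

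**If baselines differ.** Let the group means differ by D at baseline. The change-score estimate subtracts D from the post-drink difference; the adjusted estimate subtracts about rD under equal SDs. The two differ by (1 − r)D: 0.5D, 0.3D or 0.2D at r = 0.5, 0.7 or 0.8. Without randomisation, D need not be zero in expectation.

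**The case against.** The strongest reply is that the main tests are before/after comparisons within subjects, which already remove between-subject variation. The polyol-versus-glucose comparison rests on a background sentence and the cohort comparison on the SAP's change history. The study is a pilot. A t-test on changes is valid, and its loss against the adjusted model is 5% to 21% of variance for r from 0.8 down to 0.5. In non-randomised arms, the adjusted and change-score analyses can also answer different questions. All of this stands and limits the point. It does not remove it: Protocol 7.1 and 7.2 both plan between-group comparisons, and neither document says how the fasting value enters them.

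Three stronger readings are tempting, and the documents do not support them.

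- *The plan ignores the fasting platelet value.* A reader might infer this from the bare list of tests. The endpoint in Protocol 3.1 and the platelet analysis in the SAP are both written as changes, so the fasting value is used by subtraction or pairing. The larger gains against post-drink values apply only if the analyst departs from that wording.
- *Unused body weight costs precision.* Protocol 6.1 includes "Physical Exam including blood pressure, height, weight, and waist circumference" and doses are fixed in grams. But nothing in the documents shows how much variation weight explains. At 12 per group the variance ratio is (1 − R²) × 1.05: 1.05 at R² = 0, 0.945 at 0.10 and 0.84 at 0.20. Break-even is R² = 1 − 1/1.05, about 0.05. Aim 1 compares levels within each individual, so weight is not needed there.
- *Optional later draws will remove many subjects from the ANOVA.* Neither document names a complete-case repeated-measures ANOVA, and no attendance rates are given, so no loss can be calculated. The polyol-versus-glucose comparison at 30 minutes is on the day of the drink and does not depend on return visits.

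**Conclusion.** The point holds for between-group platelet comparisons only. The plan leaves open whether they use post-drink values or changes and does not use the fasting value as a covariate, although fasting blood is drawn from every subject. Relative to change scores, the likelier reading, the variance reduction is about 21%, 11% or 5% at r = 0.5, 0.7 or 0.8; the interval narrows by about 11%, 6% or 3% (one minus the square root of the variance ratio). Relative to post-drink values it is about 21%, 46% or 62%.

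These sizes rest on an assumed r, equal SDs, equal expected baselines and 12 per group. The gain is modest if changes are used and r is high. The firmer benefit is that the estimand is fixed in advance, which matters because arms are not randomised. The change is worth making; it does not call the within-subject results into question.

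**What to change.** In Protocol 7.2 and the SAP:

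1. State that between-group platelet comparisons use a linear model of the post-drink value on group plus the subject's fasting value. Apply it to each polyol versus glucose at 30 minutes in non-diabetic subjects and, if the two xylitol amounts are compared, to 30 g versus 5 g at their common times.
2. Where several times are analysed together, use the mixed-model form with all available draws.
3. Show the unadjusted difference in change beside every adjusted between-arm estimate. For diabetic versus non-diabetic, where baselines may differ by nature, keep it as a co-reported result.
4. Extend the SAP text to the glucose and 5 g xylitol arms, so that these comparisons have an analysis section.
5. If body weight is used at all, limit it to a sensitivity covariate for between-group comparisons of sweetener levels.

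The cost is wording in two documents and one error degree of freedom (22 to 21 in a two-group comparison of 12 each). No new data are needed.
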